### 12.8.2.1 Precision for adverse events

All participants will have the opportunity of receiving treatment for ligelizumab 120 mg or 240 mg in the 52 weeks of treatment period with a ratio of 50%: 50% (n=243 for each group). For each ligelizumab dose group, approximately one third of randomized participants are in each age subgroup (6-11 years, 12-17 years and 18-55 years). This yields approximately 81 participants per age group exposed with each ligelizumab dose for at least 9 months in the base case scenario.

The table below shows the sensitivity of the precision level (95% CI) based on the assumptions of different incidence rates and number of participants per age group.

**Table 12-4 Precision levels (95% CI) for sensitivity of safety incidence rate per age group**

Event rate (proportion of participants with an event)	Number of participants	95% CI
0%	81	(0, 4.5%)
1%	81	(0, 6.3%)
2%	81	(0.2%, 7.9%)
0%	162	(0, 2.3%)
1%	162	(0.1%, 4%)
2%	162	(0.4%, 5.5%)

Meanwhile, all the participants (486 participants) randomized in the study would be exposed with ligelizumab treatment for at least 9 months. For any adverse event with 1% incidence rate, the exact 95% Clopper-Pearson CI for the proportion of participants would be (0.3%, 2.3%).

Table 12-4 shows the sensitivity of the precision (95% CI) based on the assumptions of different incidence rates and total number of participants.

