#### 12.8.1 Primary endpoint(s)

The primary objective is to demonstrate that ligelizumab doses are superior to placebo in responder rate at a level of 600 mg peanut protein (1044 mg cumulative tolerated dose) after 12 weeks of treatment.

The responder rate at 600 mg dose of peanut protein in placebo and ligelizumab groups have been assumed approximately 20% and at least 80%, respectively for participants with evaluable DBPCFC at Week 12. These assumptions are considered highly clinically relevant based on the PALISADE trial conducted in similar populations ([Vickery et al 2018](#)). In the PALISADE trial, the responder rate at 600 mg single challenge dose of peanut protein in placebo and AR101 were 4.3% (95% CI: 1.9%, 9.7%) and 84.5% (95% CI: 79.9, 88.1), respectively. Approximately 15% of participants were assumed to discontinue treatment before week 12 and will be

considered non-responders in power calculations. Therefore, the responder rate at 600 mg single dose of peanut protein in placebo and ligelizumab were assumed 17% and 68%, respectively for randomized participants. For the purpose of evaluating the power for the primary trial objectives, it was assumed that none of the secondary null hypotheses would be rejected and the full alpha level of 0.025 (one-sided) would be equally split across the primary hypotheses for each dose (i.e., 0.0125 one-sided for each testing). Under the outlined assumptions, a two group Fisher’s exact test with a 0.0125 one-sided significance level will have above 99% power to detect the difference of responder rate between each ligelizumab group and placebo, when the sample size is 108 participants on each ligelizumab dose and 54 participants on placebo. In case the dosing will only be limited to 120 mg for children, the anticipated sample size also provides greater than 99% power to detect the difference of responder rate between each ligelizumab group and placebo at a 0.0125 one-sided significance level. These power calculations are an approximation of the power achieved with the logistic regression approach. The table below shows the sensitivity of the power to deviations from the assumptions.

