Safety	Treatment-emergent Adverse Events of Special Interest (AESI), by standardized MedDRA term (plus respective listing)
Safety	Number of AEs (n, %)
Safety	Newly occurring or worsening chemistry and hematology abnormalities (plus respective listing)
Safety	Newly occurring or worsening vital sign abnormalities (plus respective listing)
Safety	Adverse events for screen failures
Safety	Number of Subjects with Adjudicated Anaphylaxis Events (Safety Set) (plus respective listing)
Safety	Number of Subjects with Adjudicated CCV Events (Safety Set) (plus respective listing)
Safety	Number of Subjects with Adjudicated Neoplastic Events (Safety Set) (plus respective listing)
Safety	Number of AEs requiring Epinephrine treatment (n, %)
Disposition	Participant Disposition at Treatment Period (Randomized Set)
Set	Analysis Sets (Randomized Set)
Baseline	Subject Demographics (Randomized Set)
Baseline	Subject Baseline Characteristics (Randomized Set)

In addition, the following analyses will be presented.

DMC analyses:

The DMC will assess, at defined intervals, the progress of a clinical trial, safety data, and critical efficacy variables and recommend to the sponsor whether to continue, modify, or terminate a trial, as defined in the DMC charter. Analysis of selected efficacy variables will be provided only for the purpose of helping for safety evaluation. Such assessments do not inflate the Type I error for the primary efficacy hypothesis testing and thus no adjustment for multiplicity is required.

3 Sample size calculation

A total sample size of approximately 486 randomized participants is originally planned to achieve sufficient power for the primary and key secondary endpoints, and it provides adequate precision in estimating AE rates in this study. Due to the halt of recruitment, the sample size is now 211. This reduced sample size provides sufficient power for the primary endpoint.

Participants will receive one of three treatments (ligelizumab 240mg SCq4w, ligelizumab 120mg SCq4w, or placebo SCq4w) and will be randomized into five treatment arms with a ratio 2:2:2:2:1. At the start of the study, recruitment was restricted to participants 12-55 years old. Due to the recruitment halt, no other age groups were recruited.

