3.2.1 Precision for adverse events

Table 3-3 Precision levels (95% CI) for sensitivity of safety incidence rate for overall population

Event rate (proportion of participants with an event)	Number of participants	95% CI
0%	486	(0%, 0.8%)
1%	486	(0.3%, 2.3%)
2%	486	(1%, 3.7%)
0%	211	(0%, 1.7%)
1%	211	(0.1%, 3.5%)
2%	211	(0.6%, 4.9%)

4 Change to protocol specified analyses

On 31 March 2023, Novartis made a strategic decision to close recruitment in study CQGE031G12301 and terminate the study early. As a result, there are several changes to the specified analyses in the protocol, namely:

- Instead of 486 participants, the sample size is 211.

- There will be no recruitment of children under age 12, and the age-groups of interest are now 12-17 and 18-55.
- For participants who have reached Screening Visit 2 Part 1 and not completed Week 52 visit at the time of halt recruitment will need to complete Screening Visit 2 Part 2 to determine eligibility. If they are eligible, they will either continue treatment and perform assessments until Week 12 Part 2 or will stop treatment at the next scheduled visit if they have already completed Week 12 Part 2. This leads to limited number of participants reaching Week 52. Hence, non-inferiority test for sustainability of treatment effect at Week 52 compared to Week 12 is removed.
- Week 52 interim analysis will not be conducted.

There are also some changes made to simplify the analyses:

- Since the number of COVID-19 related intercurrent events is expected to be minimal, references to COVID-19 related intercurrent events were removed.
- Handling of intercurrent events for the secondary estimands were changed to be consistent with the primary estimand strategy.
- The two-dimensional tipping point analysis for the primary estimand was removed.

In analysis for primary estimand and secondary estimands(1, 2 and 4), log-transformed MTD at screening DBPCFC was added as covariate in logistic regression models.

The protocol mentions the summary measure of supplementary estimand is relative risk generated with a marginal standardization method. In SAP, relative risk is changed to risk difference to facilitate clinical interpretation.

5 Appendix

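### Adverse-event precision in Protocol 12.8.2.1 assumes every randomised participant reaches 9 months on ligelizumab, against the plan's own 15% discontinuation before Week 12; SAP Table 3-3 likewise counts all 211 randomised

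*Protocol*

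**What the plan says.** Protocol Section 12.8.2.1 begins with planned access to the drug: "All participants will have the opportunity of receiving treatment for ligelizumab 120 mg or 240 mg" over the 52 weeks, 243 participants per dose. It then turns this into exposure achieved. By age group it gives "approximately 81 participants per age group exposed with each ligelizumab dose for at least 9 months", and for the whole trial it says "all the participants (486 participants) randomized in the study would be exposed with ligelizumab treatment for at least 9 months". Tables 12-4 and 12-5 give 95% limits at event rates of 0, 1 and 2% for 81, 162 and 486 participants.

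Protocol Section 12.8.1 says, for power: "Approximately 15% of participants were assumed to discontinue treatment before week 12". Section 12.8.2 and Table 12-2 use the same 15%.

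After the halt, SAP Section 3 states: "Due to the halt of recruitment, the sample size is now 211". SAP Section 3.2.1 drops the age-group table and says nothing about length of exposure. Table 3-3 keeps the 486 rows and adds rows for 211. SAP Section 1.1 ends treatment at Week 12 for anyone who had not reached the Week 12 Part 2 visit at the halt. The 16-week placebo arm was due its first ligelizumab dose at Week 16. On long exposure, SAP Section 4 notes: "This leads to limited number of participants reaching Week 52".

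**The concern.** Two parts of one sample-size section use incompatible assumptions. For power, 15% of participants are lost to treatment before Week 12. For safety precision, nobody is lost for at least 9 months. A reader assessing long-term safety would take the upper limits in Tables 12-4 and 12-5 as what the trial can rule out after 9 months on drug, and for that purpose the denominators are too large.

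The SAP has a related but separate gap. Its 211 rows count everyone randomised. Because of the halt rules, some of those participants receive only placebo, so 211 is not the number exposed to ligelizumab.

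**Working it through.** **Inputs.** 486 randomised, 81 per age group and dose, and 162 (Protocol 12.8.2.1 and Table 12-4); 15% discontinuing before Week 12 (Protocol 12.8.1); 211 randomised (SAP 3) and about 23 on placebo (SAP 3.1).

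**Formula.** The upper two-sided 95% Clopper-Pearson limit is the 0.975 quantile of Beta(x + 1, n − x), with x = n × rate left as a non-integer. For x = 0 this is 1 − 0.025^(1/n).

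**Reproducing the plan.** For n = 486: 0.76, 2.34 and 3.68%. For n = 162: 2.25, 4.02 and 5.53%. For n = 81: 4.45, 6.29 and 7.92%. For n = 211: 1.73, 3.46 and 4.93%. All agree with the printed limits after rounding.

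**Applying the plan's 15%.** Someone who stops before Week 12 has at most 12 weeks on drug and cannot reach 9 months. So 486 × 0.85 = 413, 162 × 0.85 = 138, and 81 × 0.85 = 69.

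| Stated n | Printed upper limits at 0 / 1 / 2% | n after 15% | Upper limits at 0 / 1 / 2% |
|---|---|---|---|
| 486 | 0.8 / 2.3 / 3.7% | 413 | 0.9 / 2.5 / 3.9% |
| 162 | 2.3 / 4.0 / 5.5% | 138 | 2.6 / 4.4 / 6.0% |
| 81 | 4.5 / 6.3 / 7.9% | 69 | 5.2 / 7.1 / 8.7% |

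These reduced counts are ceilings. The documents give no discontinuation rate between Week 12 and Week 52, and any such loss lowers them further.

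**SAP Table 3-3.** Under SAP 1.1, a 16-week placebo participant who had not reached Week 12 Part 2 at the halt (Group 3, or Group 4 if randomised) ends treatment at Week 12, four weeks before the first ligelizumab dose. A member of that arm who had passed Week 12 Part 2 but not yet attended Week 16 falls in Group 2 and is given no drug at the next visit. The documents do not count either group. The extreme case for this arm is that none of it switched: 211 − 23 = 188. The upper limits are then 1.94, 3.69 and 5.18%, or about 1.9, 3.7 and 5.2%, against the printed 1.7, 3.5 and 4.9%. The true number in this arm who never switched lies somewhere from 0 to about 23.

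**The case against.** The strongest reply is that nothing here is miscalculated and that adverse events are analysed on the safety set, which needs only one dose of study treatment. Stopping early removes nobody from that set. That stands for crude incidence, and the reduced counts above apply only to 9-month exposure.

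Even for any ligelizumab exposure the planned loss is small. Two of the five arms, four ninths of participants, receive ligelizumab on Day 1. If every early discontinuation in the other three arms came before the first active dose, the exposed number would be 486 × (1 − 0.15 × 5/9), about 446. The upper limits would be 0.8, 2.4 and 3.8%, hardly different from Table 12-5. However, the safety set counts placebo doses as study treatment, so it does not itself supply the number exposed to ligelizumab.

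The SAP has also responded to the halt. It widens the limits to those for 211, removes the age-group table and adds exposure-adjusted incidence rates. Reported adverse-event percentages will carry exact intervals from observed data, so the planning table drives no test or decision. All of this is fair and keeps the point minor. The exposure-adjusted rates do not correct Table 3-3, which remains a table of crude proportions on everyone randomised.

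A reader might also infer that the early termination contradicts the Protocol's 9-month statement. It does not. That text belongs to Amendment 1 of April 2022, the decision to stop came in March 2023, and SAP 3.2.1 makes no 9-month claim.

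**Conclusion.** The inconsistency is real and minor. For participants with at least 9 months of exposure, the Protocol's upper limits are too favourable by 0.1 to 0.2 percentage points overall and by about 0.8 points per age group and dose. This rests on the plan's own 15%, applied equally to all arms and age groups, with no further loss after Week 12. The intervals themselves are correct for the n they state.

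In the SAP, the 211 rows overstate the number exposed to ligelizumab by an unknown amount. If the whole 16-week placebo arm went unswitched, the upper limits rise by about 0.2 to 0.3 points.

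It is tempting to go further and say that most remaining participants stopped well before 9 months. The documents do not support that: they give neither the number in each halt group nor an enrolment timeline, only that few reach Week 52. No precision for 9-month exposure after the halt can be calculated from what is published.

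**What to change.** - In Protocol 12.8.2.1, replace the claim that everyone reaches 9 months with planned exposure for those who complete treatment. Restate the 9-month limits on 413, 138 and 69. If no further amendment is planned, record the correction in SAP Section 4.
- In SAP Table 3-3, base the post-halt rows on the number who received at least one ligelizumab dose, and label them so.
- Add a separate row for the number actually exposed for at least 9 months, taken from the dosing records.

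The cost is one sentence and one table, with slightly less favourable figures. No analysis, test or data collection changes.

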**Table 12-5 Precision levels (95% CI) for sensitivity of safety incidence rate for overall population**

Event rate (proportion of participants with an event)	Number of participants	95% CI
0%	486	(0, 0.8%)
1%	486	(0.3%, 2.3%)
2%	486	(1%, 3.7%)

## **13 Ethical considerations and administrative procedures**

### **13.1 Regulatory and ethical compliance**

This clinical study was designed and shall be implemented, executed and reported in accordance with the ICH Harmonized Tripartite Guidelines for Good Clinical Practice, with applicable local regulations (including European Directive 2001/20/EC, US CFR 21), and with the ethical principles laid down in the Declaration of Helsinki.

### **13.2 Responsibilities of the investigator and IRB/IEC**

Before initiating a trial, the investigator/institution must obtain approval/favorable opinion from the Institutional Review Board/Independent Ethics Committee (IRB/IEC) for the trial protocol, written informed consent form, consent form updates, participant recruitment procedures (e.g., advertisements) and any other written information to be provided to participants. Prior to study start, the investigator is required to sign a protocol signature page confirming his/her agreement to conduct the study in accordance with these documents and all of the instructions and procedures found in this protocol and to give access to all relevant data and records to Novartis monitors, auditors, Novartis Quality Assurance representatives, designated agents of Novartis, IRBs/IECs, and regulatory authorities as required. If an inspection of the clinical site is requested by a regulatory authority, the investigator must inform Novartis immediately that this request has been made.

### **13.3 Publication of study protocol and results**

The protocol will be registered in a publicly accessible database such as clinicaltrials.gov and as required in EudraCT. In addition, after study completion (defined as last participant last visit) and finalization of the study report the results of this trial will be submitted for publication and posted in a publicly accessible database of clinical trial results, such as the Novartis clinical trial results website and all required Health Authority websites (e.g. Clinicaltrials.gov, EudraCT etc.).

For details on the Novartis publication policy including authorship criteria, please refer to the Novartis publication policy training materials that were provided to you at the trial investigator meetings.

### **13.4 Quality Control and Quality Assurance**

Novartis maintains a robust Quality Management System (QMS) that includes all activities involved in quality assurance and quality control, to ensure compliance with written Standard Operating Procedures as well as applicable global/local GCP regulations and ICH Guidelines.

Audits of investigator sites, vendors, and Novartis systems are performed by auditors, independent from those involved in conducting, monitoring or performing quality control of the clinical trial. The clinical audit process uses a knowledge/risk based approach.

Audits are conducted to assess GCP compliance with global and local regulatory requirements, protocols and internal SOPs, and are performed according to written Novartis processes.

### **13.5 Participant Engagement**

Participant engagement initiatives are included in this study and will be provided, for distribution to study participants. If compliance is impacted by cultural norms or local laws and regulations, sites may discuss modifications to these requirements with Novartis.

- Thank You letter
- Plain language trial summary - after CSR publication
- Trial Feedback Questionnaires (TFQ)

## **14 Protocol adherence**

This protocol defines the study objectives, the study procedures and the data to be collected on study participants. Additional assessments required to ensure safety of participants should be administered as deemed necessary on a case by case basis. Under no circumstances including incidental collection is an investigator allowed to collect additional data or conduct any additional procedures for any purpose involving any investigational drugs under the protocol, other than the purpose of the study. If despite this interdiction prohibition, data, information, observation would be incidentally collected, the investigator shall immediately disclose it to Novartis and not use it for any purpose other than the study, except for the appropriate monitoring on study participants.

Investigators ascertain they will apply due diligence to avoid protocol deviations. If an investigator feels a protocol deviation would improve the conduct of the study this must be considered a protocol amendment, and unless such an amendment is agreed upon by Novartis and approved by the IRB/IEC and Health Authorities, where required, it cannot be implemented.

### **14.1 Protocol amendments**

Any change or addition to the protocol can only be made in a written protocol amendment that must be approved by Novartis, health authorities where required, and the IRB/IEC prior to implementation.

Only amendments that are required for participant safety may be implemented immediately provided the health authorities are subsequently notified by protocol amendment and the reviewing IRB/IEC is notified.

Notwithstanding the need for approval of formal protocol amendments, the investigator is expected to take any immediate action required for the safety of any participant included in this study, even if this action represents a deviation from the protocol. In such cases, Novartis should be notified of this action and the IRB/IEC at the study site should be informed according to local regulations.

## 16 Appendices

### 16.1 Appendix 1: Clinically notable laboratory values and vital signs

#### Laboratory assessments

Refer to [Section 16.2](#) for clinically notable laboratory values for hepatotoxicity.

Refer to [Section 16.3](#) for clinically notable laboratory values for nephrotoxicity

The following other specific criteria have been identified for this study:

- Platelets < 75 000/ $\mu$ L
- Any participant who has platelets < 75 000/ $\mu$ L after being randomized should discontinue study treatment.

For all other laboratory assessments, the Central Laboratory will flag laboratory values falling outside of the normal ranges on the Central Laboratory Report (which the investigator should review and sign-off) and the investigator will report any values considered clinically significant in the CRF.

#### Vital signs

Notable values for vital signs for adults are:

- heart rate of < 60 and > 100 bpm
- systolic blood pressure of < 90 and  $\geq$  140 mmHg
- diastolic blood pressure of < 60 and  $\geq$  90 mmHg

For children (6-11years) and adolescents, the notable values are described in [Table 16-1](#):

**Table 16-1 Notable values for Heart Rate (HR) and Blood Pressure in children and adolescents**

	HR (bpm)			
Age range	Low		High	
6-8 years	<74		>111	
8-12 years	<67		>103	
12-15 years	<62		>96	
$\geq$ 15 years	<58		>92	
Age (years)	Blood pressure (mmHg)			
	Boys		Girls	
6	105	66	105	67
7	106	68	106	68
8	107	69	107	69
9	107	70	108	71
10	108	72	109	72
11	110	74	111	74
12	113	75	114	75
13	120	80	120	80
Heart Rate (HR) Adapted from Fleming et al 2011 ; Blood Pressure (BP) adapted from Flynn et al 2017				

## **ECG**

For adults, a notable QTc value is defined as a QTcF (Fridericia's) interval of greater than 450 ms for males or greater than 460 ms for females – all such ECGs will be flagged by the Central CRO's cardiologist and require assessment for clinical relevance by the investigator.

For children, a QTc  $\leq$ 450 ms is recommended as the upper limit of normal for children up to 12 years of age. In children older than 12 years, the same thresholds apply as for adults i.e. QTc <450 ms in males and QTc <460 ms in females (Novartis ECG and QTc Clinical Development Safety Guideline, 2017)

## 16.2 Appendix 2: Liver event and laboratory trigger definitions & follow-up requirements

**Table 16-2 Liver event and Laboratory trigger definitions**

	Definition/ threshold
Liver laboratory triggers If ALT, AST and total bilirubin normal at baseline:	
 
· ALT or AST > 5 × ULN
 
· ALP > 2 × ULN (in the absence of known bone pathology)
 
· Total bilirubin > 3 × ULN (in the absence of known Gilbert syndrome)
 
· ALT or AST > 3 × ULN and INR > 1.5
 
· Potential Hy's Law cases (defined as ALT or AST > 3 × ULN and Total bilirubin > 2 × ULN [mainly conjugated fraction] without notable increase in ALP to > 2 × ULN)
 
· Any clinical event of jaundice (or equivalent term)
 
· ALT or AST > 3 × ULN accompanied by (general) malaise, fatigue, abdominal pain, nausea, or vomiting, or rash with eosinophilia
 
· Any adverse event potentially indicative of a liver toxicity*
 

If ALT or AST abnormal at baseline:	
 
· ALT or AST > 2x baseline or > 300 U/L (whichever occurs first)
 

*These events cover the following: hepatic failure, fibrosis and cirrhosis, and other liver damage-related conditions; non-infectious hepatitis; benign, malignant and unspecified liver neoplasms ULN: upper limit of normal
	

